The primary endpoint is 6-months post-randomisation. All participants (in both trial arms) will complete assessments at baseline, 6- and 12-months post-randomisation. A number of participants (parents and adolescents), and key stakeholders will be invited to participate in semi-structured interviews to ascertain acceptability and their experience of the intervention, while we will also develop specific target indicators drawn from our logic model which will we measure during the trial.

Intervention – Standard Teen Triple P

Standard Teen Triple P is a targeted-indicated intervention for parents of an adolescent child, aged up to 16 years. The programme is indicated for parents who are concerned about their teenager's development and behaviour.

Standard Teen Triple P involves a thorough assessment of the parent-child relationship, and the application of parenting skills to a broad range of target behaviours. The programme involves parents attending 10 (1-hour) one-to-one sessions, where they learn practical strategies for how to manage their child's problematic behaviour, promote healthy development, and improve the quality of the parent-child relationship. Sessions are delivered face-to-face, either in person or via video-conferencing. All parents will be invited to attend sessions.

Practitioners use a range of learning methods, including behavioural rehearsal to teach parents new skills, guided participation to discuss assessment findings, active skills training methods to facilitate the acquisition of new parenting routines, and generalisation-enhancement strategies to promote parental autonomy.

In addition, parents are continuously provided with constructive feedback and are encouraged to set goals, practice strategies, and complete their activity workbook and homework tasks.

Sessions 1-3 are set-aside for assessment. In session 1, parents are interviewed to obtain information regarding the current problem, the teenager's developmental history and the family history. If possible, session 2 involves an interview with the teenager and an observation

of the parent-child interaction. Then, in session 3, the practitioner shares assessment findings and assists the parent(s) to set goals.

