A final Statistical Analysis Plan will be produced prior to any analysis being undertaken and will provide detail of handling missing data. We will explore the impact of missing data on trial outcomes by investigating likely missing data mechanisms and re-fitting the primary outcome within a multiple imputation framework (including exploring MAR and MNAR mechanisms via delta-based controlled multiple imputation).

Procedures for reporting deviation(s) from the original SAP

Any deviations from the original SAP will be submitted as substantial amendments where applicable and recorded in subsequent versions of the protocol and SAP.

Termination of the trial

Beyond the internal pilot, there will be no formal 'stopping rules' or 'discontinuation criteria' for individual participants, parts of trial and entire trial. Any concerns with participant well-being will cross reference this section with those for the TSC as this group is likely to be involved with this decision-making process.

Continuation of the trial from internal pilot to main trial will be decided by the Trial Steering Committee and funder at month 12 (see Internal Pilot Section).

Inclusion in analysis

All randomised participants' data will be included in analysis, if consent has been obtained to use their data and have not withdrawn from the trial, and they have not withdrawn consent to use their data.

Internal Pilot analysis

Statistical analysis for internal pilot feasibility outcomes will be primarily descriptive. Feasibility outcomes will be estimated as frequencies and percentages, means and standard deviations, or medians and interquartile ranges as appropriate. Feasibility outcomes will be assessed against the pre-specified progression criteria. Percentage of missing data will also be reported descriptively.

Analysis of primary and secondary outcomes

Our primary analysis will include all randomised participants who provide outcome data (i.e., a modified intention to treat analysis set) and compare mean scores between arms on the parental SDQ total problems score at 6-months post-randomisation (including both parents' ratings where available) using multilevel models to account for clustering (parents in families), and adjusting for baseline SDQ score, adolescent factors (age, sex, parents in household), and local authority.

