Deviations from the protocol which occur frequently will be addressed immediately and if appropriate will be classified as a serious breach.

The final analysis will also present the proportions of protocol deviations in a table (following intention to treat principle).

Analysis population

Parents and foster carers identified by case-holding social workers and edge of care teams across six local authorities (Cambridgeshire, Peterborough, Birmingham, Gloucestershire, London Borough Merton, and Wirral) and their young people aged 11-15 years and at the edge of care. The intention-to-treat population will include all randomised patients, according to the treatment they were randomised to receive.

Study population

Screening data

The following summaries will be presented for all screened Parents/ carers and Young people (overall and by local authority):

Enrolment: the number of days recruiting, the number of Parents/carers/CYP screened, the number of Parents/carers/CYP recruited, the number of screened Parents/carers/CYP not recruited, and the reason for non-recruitment.

This information will be included into the CONSORT flow diagram (see appendix for template).

Eligibility

Families are eligible for the trial if they meet all the following inclusion criteria and none of the exclusion criteria apply. All queries about family eligibility should be directed to the Trial Manager before randomisation/recruitment.

Definition of *Edge of Care*

Edge of Care refers to children/young people who either:

- have not entered into care as they have been assessed and the LA has chosen to support them and their families through alternative provisions/services. Or
- they are being considered for care but have not entered into local authority care.

Inclusion criteria

- Families of young people aged 11-15 years (inclusive) determined as being on the *edge of care*

Exclusion criteria

- Families where one or more parent has received a multi-session parenting programme covering similar content to Triple P over the previous 12 months
- Families where one or more parent is currently receiving a multi-session parenting programme covering similar content to Triple P or any multi-component manualised family intervention, such as Multi-Systemic Therapy

The number of ineligible participants randomised, if any, will be reported, with reasons for ineligibility. Ineligible participants will be removed from the data and not included into the analysis.

Recruitment

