A CONSORT flow diagram (appendix A) will be used to summarise the number of CYP who were:

- assessed for eligibility at screening
- eligible at screening
- ineligible at screening*
- eligible, consented and randomised
- eligible but not randomised*
- received the randomised allocation
- did not receive the randomised allocation*
- lost to follow-up*
- discontinued the intervention*
- randomised and included in the primary analysis
- randomised and excluded from the primary analysis*

*reasons will be provided.

Withdrawal/Follow up

Level of withdrawal

The participants service as usual will not be affected at any time by declining to participate or withdrawing from the trial because they will still receive services as usual. If a participant initially consents but subsequently withdraws from the trial, clear distinction will be made as to what aspect of the trial the participant is withdrawing from. These aspects will be:

- Withdrawal from intervention (TEEN TRIPLE P only)
- Partial withdrawal from future follow-up data collection (e.g., some questionnaires, interviews)
- Withdrawal from previously collected data, prior to data analysis

Participants cannot withdraw from the trial but still receive the intervention, if they withdraw from the trial then they will receive usual services only. All participants will be included in the primary analysis unless they withdraw their consent for the use of their data.

Timing of withdrawal

Participants have the right to withdraw consent for participation in any aspect of the trial at any time.

Reasons for withdrawal

Participants who consent and subsequently withdraw should complete the trial withdrawal form or the withdrawal form should be completed on the participant's behalf by the site staff/trial team based on information provided by the participant. This withdrawal form should be sent to the Trial email address. Any queries relating to potential withdrawal of a participant should be forwarded to the Trial Manager.

Presentation of withdrawal/Loss to follow up

The number and % of participants that have withdrawn/loss to follow up from the study will be presented in a table for all stages. Results will be provided by treatment group.

Baseline participant characteristics

List of baseline data

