- Delinquency – the Self Report Delinquency Measure: Baseline and 12 month follow up data will be collected. Baseline and 12-month follow up data will only be used in the 12 month followup addendum report. The SRDM is a derived total score following Smith & McVie (2003) and the units are a relative measure of delinquency. The SDRM is a measure comprising 15-items pertaining to antisocial behaviours (e.g., burglary, violence). It requires CYP to respond with yes or no with reference to a time-period (6 months). They then report the estimated frequency of the behaviour, and whether they have ever been caught. Each items frequency is scored 0-5, 6-10 is scored 6 and 11+ is scored 11. Minimum score would be 0 and maximum number of delinquent behaviours would be 165 (15x11). On this basis, we are likely to have a skewed continuous distribution, so some transformation may be required after inspection of model residuals. In addition, there may be a number of individuals where this is their first time in a custody unit, so there is a possibility of floor effects depending on the

frequency of their delinquent behaviour. A higher number of delinquent behaviours is bad, so a reduction in the outcome indicates an effective treatment.

Analysis methods

List of methods and presentation

Internal pilot study

Statistical analysis for internal pilot feasibility outcomes will be primarily descriptive. Feasibility outcomes (primary outcome measures and all secondary measures) will be estimated as frequencies and percentages, means and standard deviations, or medians and interquartile ranges as appropriate. Feasibility outcomes will be assessed against the pre-specified progression criteria.

Primary analysis (6 month)

Our primary analysis will include all randomised participants who provide outcome data (i.e., a intention to treat basis) and compare mean scores between arms on the SDQ externalising behaviour at 6-months post-randomisation using a linear mixed model, adjusting for baseline SDQ score and local authority. A random intercept will also be included to account for family level clustering at level 2 (individual at level 1 and family at level 2).

$$L1: Y_{ik} = \beta_{0k} + \beta_{1k}SDQ_BL_{ik} + \beta_{2k}local_authority_{ik} + r_{ik}, \quad r_{ik} \sim N(0, \sigma^2)$$

$$L2: \beta_{0k} = \gamma_{00} + \gamma_{20}TX_k + \mu_{0k}, \quad \mu_{0k} \sim N(0, \tau_2^2)$$

$$\beta_{1k} = \gamma_{10}$$

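### The SAP defines intention to treat as everyone randomised, then deletes randomised participants found ineligible, with no safeguard on how or when ineligibility is judged

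*SAP*

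**What the plan says.** Four statements in the SAP bear on who is analysed.

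- Analysis population: "The intention-to-treat population will include all randomised patients, according to the treatment they were randomised to receive".
- Study population, Eligibility: "The number of ineligible participants randomised, if any, will be reported, with reasons for ineligibility". The next sentence is: "Ineligible participants will be removed from the data and not included into the analysis".
- Level of withdrawal: "All participants will be included in the primary analysis unless they withdraw their consent for the use of their data".
- Primary analysis (6 month): "Our primary analysis will include all randomised participants who provide outcome data (i.e., a intention to treat basis").

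The protocol has two relevant statements. Its section on primary and secondary outcomes describes the primary set as "all randomised participants who provide outcome data (i.e., a modified intention to treat analysis set"). Its Inclusion in analysis section keeps randomised participants only if they have agreed to data use, "have not withdrawn from the trial, and they have not withdrawn consent to use their data".

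On conduct, the protocol's Blinding section leaves families, practitioners and the Trial Manager unblinded. Both documents send eligibility queries to the Trial Manager before randomisation or recruitment. Neither says who decides if the question arises afterwards.

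**The concern.** Because the sentence about deletion follows one about ineligible people who were randomised, it is an exclusion made after allocation. Such exclusions can be defended when they rest only on facts fixed before randomisation, are judged by someone who does not know the arm, and have a cut-off. The SAP states none of these conditions. Its Sensitivity analyses section plans no run that restores the deleted cases, and the sentence on reporting does not ask for counts by arm.

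Information about eligibility could also reach the team differently in the two arms. Only intervention families have Teen Triple P assessment sessions. In the first of these, "parents are interviewed to obtain information regarding the current problem", together with developmental and family history. A similar parenting programme in the previous 12 months is an exclusion criterion and could come to light there. The opposite direction is possible too. The protocol's Contamination section says that SAU-only families may receive other parenting interventions after recruitment. Without a date restriction, the criterion on current programmes could be misapplied to them.

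At stake are the composition of the primary analysis set, a possible bias in either direction, and a result labelled intention to treat that would not be.

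**Working it through.** **1. Apply each rule to the same case.** Take a family that is randomised, later found ineligible, gives 6-month data and permits their use.

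- SAP, Analysis population: in.
- SAP, Level of withdrawal: in.
- SAP, Primary analysis (6 month): in.
- SAP, Eligibility: out.

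Two analysts could build different primary datasets from this SAP.

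Now take an eligible family that gives 6-month data, then leaves the trial but still permits use of its data. The protocol's Inclusion in analysis section puts it out; the SAP puts it in.

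**2. Reproduce the planning figure.** Inputs from the sample size sections of both documents: effect 0.35 SD, two-sided alpha 0.05, power 0.90, baseline correlation 0.5, ICC 0.5, average cluster size 1.5, loss 20%.

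- Unadjusted n per arm: 2 × (1.960 + 1.282)² / 0.35² gives 172 (172.5 with the t distribution).
- Baseline adjustment: 1 − 0.5² = 0.75.
- Design effect: 1 + (1.5 − 1) × 0.5 = 1.25.
- 172 × 0.75 × 1.25 = 161.25, and 161.25 / 0.80 = 201.6 per arm, or 404 in total. The t version gives 406, and rounding up at each step gives 408. The stated 412 is within 2% of all three.

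No stated number is wrong, and the fix leaves 412 unchanged.

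**3. Precision at the planned size.** Analysed per arm: 206 × 0.8 = 164.8. SE = √0.75 × √(2 × 1.25 / 164.8) = 0.107 SD. Power is 0.907.

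**4. Effect of deletion in one arm (assumed inputs).** Suppose a share f of the intervention arm is deleted and those families score k SD worse than the families that remain, whose mean is μ. The full-arm mean is (1 − f)μ + f(μ + k) = μ + fk. After deletion it is μ, so the shift is fk. The documents equate 0.35 SD with about 2 points, which implies an SD of 2 / 0.35 = 5.7 points.

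- f = 5%, k = 0.5: 0.025 SD, 0.14 points, 7% of 0.35; two-sided type I error 0.056.
- f = 10%, k = 0.5: 0.05 SD, 0.29 points, 14%; type I error 0.0755.
- f = 10%, k = 1: 0.10 SD, 0.57 points, 29%; type I error 0.155.
- f = 2%, k = 0.25: 0.005 SD, 1%; type I error 0.050.

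The type I errors set the unadjusted shift against the SE in step 3.

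**5. Baseline adjustment.** Assume the deleted families have the same excess k at baseline and the slope is 0.5 (the planning correlation, with equal SDs). The adjusted excess is then k − 0.5k = 0.5k and each shift halves. The first three cases become 0.0125, 0.025 and 0.05 SD, with type I error of 0.0516, 0.056 and 0.0755.

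**6. Effect of deletion in both arms.** If a further 2%, 5% or 10% were removed from each arm, power would fall from 0.907 to 0.901, 0.892 or 0.876.

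**The case against.** The strongest reply is that the rule will rarely operate. Case-holding social workers or edge-of-care teams screen families, and eligibility is checked again after consent and before randomisation. Waivers are barred. The SAP itself treats ineligible randomised cases as something that may not arise. Deleting 5–10% of the intervention arm would mean about 10–21 of 206 parents, and nothing in the documents supports that rate. The rule is also prespecified, numbers and reasons are to be reported, and the CONSORT diagram lists those randomised but left out of the primary analysis. All of this stands and limits the likely size. None of it says that such cases stay in the analysis, so the contradiction remains.

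Three stronger readings are tempting, but the documents do not support them.

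- *A reader might infer that ineligibility will be discovered mainly in the intervention arm.* The description of session 1 mentions neither earlier programmes nor any re-check of eligibility. Families in both arms are known to local-authority staff and receive existing services. A one-arm route is plausible; that it dominates is not shown.
- *A reader might count entry to care as a late-discovered ineligibility.* Out-of-home placement after randomisation is an outcome, recorded at each follow-up in both arms, and removal from the family home is listed as an adverse event. Neither is an eligibility failure.
- *A reader might say that the protocol's withdrawal rule breaks the stated intention-to-treat analysis.* The protocol calls its own set modified intention to treat and leaves the handling of missing data to the final SAP. The SAP already holds the acceptable rule. Because both primary sets need outcome data, the two rules differ only for people who withdraw after giving 6-month data. This is a conflict to tidy up, not a breach.

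**Conclusion.** The SAP is wrong as written. Its instruction to delete ineligible randomised participants cannot be reconciled with its definition of intention to treat, its withdrawal rule or its primary analysis set. The missing conditions on timing, evidence and blinding make arm-dependent exclusion possible. That it will happen, and how often, is not established.

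The size rests wholly on assumed exclusion rates and outcome differences, with all deletions in one arm. Unadjusted, it is 0.025–0.05 SD for 5–10% at 0.5 SD, and 0.10 SD at 10% and 1 SD. It is about half that under the baseline-adjustment assumptions in the working, and negligible if exclusions are rare. The case for change rests on the contradiction and the low cost of removing it, not on an expected large bias. The withdrawal conflict and the differing labels are secondary.

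**What to change.** In the SAP's Eligibility section, replace the deletion sentence with: *Randomised participants later found ineligible are reported by arm with reasons and kept in the primary analysis as randomised; a sensitivity analysis excludes those shown, from pre-randomisation facts judged blind to arm, to have been ineligible.* The person making that judgement should be named and should not be the Trial Manager, who knows the allocation.

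As secondary alignment, amend the protocol's Inclusion in analysis section to match the SAP's Level of withdrawal section, so that only withdrawal of consent to data use removes data already collected. Use one label for the primary set in both documents.

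The cost is a few sentences of text and one extra sensitivity run. The sample size does not change.
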